staff versus testing only symptomatic students and staff. In this proposal, 12 middle and high schools from five predominantly African-American school districts in the St. Louis metropolitan area will be cluster randomized to screening testing plus symptomatic testing versus symptomatic testing alone. We will perform qualitative listening sessions and interviews with members of the school community including parents, teachers, administrators, and students to understand the facilitators and barriers to testing, the concerns regarding in-person school, and potential issues involving vaccine hesitancy evident in all populations and groups.

This study will provide critically needed, rigorous data to inform the utility of screening testing in schools and if it is important in aiding schools in the African-American community to return to in-person instruction. Additionally, the measurements of school-based transmission rates will help participating schools in the African-American community assess the impact of their mitigation strategies, demonstrate potential risk points for transmission that can be targeted for further intervention, and reassure the community on the safety of their schools. Finally, the study results will aid participating researchers, school districts and communities in understanding how to mitigate concerns about in-person schooling and the reliability of the mitigation strategies (with or without screening testing) in preventing COVID-19 transmission.

B Background

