| Consent students and staff to receive surveillance testing | • | | | | | | | |
| Conduct surveillance testing in select schools | • | • | • | • | | | | |
| Assess school-based transmission with use of testing | • | • | • | • | • | | | |
| Collect weekly number of school cases, contacts, and in-person enrollment | • | • | • | • | | | | |
| Analyze testing data | | | | | • | • | | |
| Conduct listening sessions & Interviews | • | | | • | | | • | |
| Conduct qualitative analysis | | • | | | • | | | • |
| Share data with Duke coordinating center | • | • | • | • | • | • | • | • |
| Disseminate results | | | • | | • | | | • |

In this proposal, quantifiable milestones will be established in regards to testing. We propose that in the first 3 months post award (Q1), we will perform approximately 3,000 tests. In Q2 and Q3, we estimate approximately 5,000 and 8,000 tests will be performed. In Q4, forecasting a potential winter surge of COVID-19, we estimate a total of 10,000 tests. We estimate that approximately 50%-60% of the testing will occur in adult school staff members based on our current RADx-UP experience. Since we are primarily testing in middle and high schools, approximately 30%-40% of the tests will be done in students between the ages of 11 and 18 years of age.

We have established a process with our testing lab, informatics professionals, and study team to reliably obtain tests; however, trust in the test and the importance of testing will be important to maximize participation. We will work closely with our CAB, community partners, and messaging experts to mitigate this risk and maximize participation. Finally, we have identified additional schools to participate if one or more of the selected schools remain virtual, but could also include these additional schools if testing volume in the core schools proves to be lower than expected.

Study Setting and Populations.

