The following five school districts in St. Louis County will be included: University City, Ferguson-Florissant, Normandy, Pattonville, and Jennings. Individuals who are students, staff, and household members of students and staff are eligible to participate in the various parts of the study. Sixteen middle and high schools from these school districts will participate. According to St. Louis County and regional hospital data, these districts are located in areas that have been most heavily impacted by COVID-19, especially in the early months of the pandemic. Additionally, all schools in this study receive Title 1 funding and have 100% of their students receiving free and reduced lunch. The percent of in-person attendance when available ranges from 20%-42%, and 18%-42% of families in these districts live below the poverty line.

D Study Procedures

D1 Testing Study Procedures

Recruitment and Consent

All research activities will occur among the students, parents/guardians, staff (teachers, aides, nurses, administrators) and household members of our participating school districts. All students (5-21 years old), school staff, and their household members (all ages) are eligible for inclusion in the study. Individuals will be excluded if they (or their parents/LAR) do not provide consent or are unable to provide saliva for testing.

Screening Testing Consent

Prior to starting screening testing, students, staff, and their household members will be consented or assented in-person (group or individual discussion), by phone, or by zoom. Middle and high school students under the age of 18 will provide assent (if cognitively able) for participation after we have obtained consent from their parent/LAR by phone, zoom or in person. Since household members/parents/LARs are not present in the school, they may receive a copy of the consent document prior to the consent discussion.

Symptomatic/Exposure Testing Consent

For symptomatic and/or exposure testing, we will obtain verbal consent and assent (when appropriate) prior to testing. A copy of the consent information will be provided. We will also have individuals sign an email communication form and note their email preferences. The email communication form might be in person or electronic since parents/LARs are not present at the school.

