Symptomatic and/or Exposure Testing: All schools participating in the study will have access to ShieldT3 saliva SARS-CoV-2 PCR testing for students, staff, family members, and/or household members who exhibit symptoms of COVID-19 or have a known exposure. This testing will be provided for both virtual and in-person staff and students. Test samples will be collected in a designated area in each school building for those individuals attending or working in the in-person environment.. For those in virtual learning, or those who are family members and/or household members a drive-up testing area will be available at each site. In situations where transportation is limited, home visits will be offered.

Contact/Data Elements Survey:

Case/Contact Interviews

If any of these individuals or other students/staff present in the school setting are positive for COVID-19, contact tracing will be performed by their school districts per local/state guidance. As part of their contact tracing, individuals will be informed that they may be contacted by a member of the study team to see if they would like to provide additional information via participating in our research. Our research team will contact any cases and their known contacts in the school setting, as provided by the schools. After consent and assent (for those 8-17) is obtained, we will ask them the types of questions listed below. A separate case interview will also be conducted for any known contacts that have a subsequent positive COVID test.

Data Elements Survey

Those who have signed a consent for screening testing will be asked these data elements. Additionally, anyone who has symptomatic testing performed for the purpose of this study and/or was identified during contact tracing, will be asked to provide additional information via participating in our research. Once consent [consent information sheet 14Apr2021] is obtained via phone, Zoom, email or in person, we will ask them questions. Individuals who have agreed to referral and indicate certain needs or resource limitations will be referred to community partners. This will be done through information being provided to the community partner for follow up with the individual.

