The questions in both of these include those related to: housing, employment, health insurance, languages spoken in the home, family income, work PPE and distancing, vaccinations, reasons for getting/not getting a COVID-19 vaccine, alcohol and tobacco/nicotine use, previous COVID-19 testing, accessibility to testing, perceived accuracy of testing, perceived benefits of testing, perceived risks of testing, intention to be testing, food insecurity, trust of sources to provide correct information about COVID-19, height, weight, health status, teacher or student, grade taught/ grade student is in, type of learning, classroom setting, sports/ band/choir/drama/clubs participation, before or after school program, percent of time spent closer than 6 feet to others, percent of time mask is worn, percent of time able to social distance, access to handwashing, COVID symptoms, quarantine status/length, COVID test results, type of test, last day in person school, mitigation strategies by the individual/case at school, exposures outside school setting in the 14 days prior to exposure (contact) or 2 days prior to symptom onset (COVID sample if asymptomatic) (case) up until isolation, mask/social distance used at outside school settings. To reduce the length of the interview, these individuals will also be asked to complete some questions via RedCap.

Screening Testing: Schools will be randomized to perform or not perform weekly saliva-based screening testing for students and staff in addition to symptomatic testing. Eight of the sixteen schools will be randomized to screening testing.

Students, staff, and household members attending in-person school will be offered weekly screening testing if they (or their household member) are attending a school randomized to this strategy. Prior to the start of screening testing, participants will provide informed consent/assent and demographic information. The saliva-based testing method will allow for staff and students to obtain the sample at home or school, then give it to school personnel; study team members will label and transport the specimens for testing to the WUSTL laboratory. Weekly screening testing will be available whenever in-person school is provided for schools randomized to this strategy, including during summer sessions.

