Power calculation: A cluster randomized trial (CRT) will be conducted at 12 schools that provide symptomatic SARS-CoV-2 testing to students and staff. Schools will be randomized 1:1 to either screening testing plus symptomatic testing, or symptomatic testing only. All participants including students and staff will receive the same assignment within a given school. The primary outcome is transmission rate, defined as the ratio of the number of contacts testing positive for SARS-CoV-2 to total number of contacts for each school-based case. We hypothesize that schools performing screening testing will have lower transmission rates than routine symptomatic testing. We expect that transmission rates with screening testing or routine symptomatic testing will be 2% and 8%, respectively. With the assumptions that the intracluster correlation coefficient (ICC) is 0.02 and the standard deviation of transmission rate is 0.22, 6 schools in each arm with an average of 117 participants per school will achieve 80% power to detect a difference in transmission rates between the two study arms using a two-sided t-test at a significance level of 0.05 (Table 3). PASS 15.0 was used to conduct this power analysis.

Table 3. Sample Size

| ICC | Standard deviation | # of participant per school |
|------|--------------------|-----------------------------|
| 0.01 | 0.25 | 83 |
| | 0.30 | 188 |
| | 0.33 | 376 |
| | 0.35 | 803 |
| 0.02 | 0.22 | 117 |
| | 0.23 | 164 |
| | 0.24 | 252 |
| | 0.25 | 486 |
| 0.03 | 0.20 | 221 |
| | 0.21 | 806 |

Analysis plan: The generalized estimating equation (GEE) model with appropriate link function (e.g., identity for primary outcome) will be used to analyze the CRT data, in which the correlation among participants within each school needs to be considered. The autoregressive of first order as a working correlation structure will be used, and participants with missing values will be excluded from the GEE analysis. The GEE model includes the group indicator and other potential factors, including: race/ethnicity, insurance status, age, gender, underlying diagnoses, masking, distancing, ventilation, location of transmission. Least square means for the primary outcome per group will be estimated, and the standard errors will be calculated with the GEE sandwich method when accounting for within-school correlation. All analyses will be conducted using SAS (SAS Institute, Cary, NC) at the two-sided significance level of 0.05.

Data Management.

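### Allocation of 12 (or 16) schools is described only as 1:1, with no balancing on district or middle/high level, which leaves avoidable between-school variance and chance imbalance

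*Combined protocol and SAP*

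**What the plan says.** Allocation is described in two places. Section E (Power calculation) says "Schools will be randomized 1:1 to either screening testing plus symptomatic testing, or symptomatic testing only". Section D1 (Screening Testing) says "Schools will be randomized to perform or not perform weekly saliva-based screening testing for students and staff in addition to symptomatic testing", followed by "Eight of the sixteen schools will be randomized to screening testing". Neither mentions stratification, matching, minimization or constrained randomization.

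The number of schools is inconsistent and must be reconciled. The Introduction has "12 middle and high schools from five predominantly African-American school districts" and section E also uses 12, whereas Study Setting and Populations says "Sixteen middle and high schools from these school districts will participate".

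The primary outcome in section E is, for each school-based case, the share of its contacts who test positive. On who finds those contacts, section D1 (Case/Contact Interviews) says "contact tracing will be performed by their school districts per local/state guidance". Assessment of School-based Transmission gives the task to school staff and administrators.

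The Analysis plan lists race/ethnicity, insurance status, age, gender, underlying diagnoses, masking, distancing, ventilation and location of transmission as possible GEE covariates. District and middle/high level are not listed.

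Schools may be added later. The milestones text says the study "could also include these additional schools if testing volume in the core schools proves to be lower than expected", and section D1 allows further districts to join if one stops in-person teaching.

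**The concern.** With 12 or 16 units, 1:1 allocation fixes the number of schools per arm and nothing else. Two known groupings of the schools could plausibly affect the outcome. District may affect how contacts are traced and tested. Level goes with age, timetable and extracurricular exposure. If a district's schools fall in one arm, the realised comparison partly mixes screening with whatever distinguishes that district, and no listed covariate represents tracing practice.

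The second cost is precision. School-to-school variation that balancing could take out of the comparison stays in its standard error. In a trial of this size that is the larger part of the error.

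**Working it through.** **Inputs.** From section E: difference 0.08 − 0.02 = 0.06, SD 0.22, ICC 0.02, m = 117 per school, K = 6 schools per arm, two-sided 0.05. From section D1: K = 8 as the alternative. District sizes, the middle/high split and the share of variance that balancing removes are not in the document. They are assumed below and shown as ranges.

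**1. The plan's own power.** Design effect = 1 + (117 − 1) × 0.02 = 3.32. SE = 0.22 × √(2 × 3.32 / (6 × 117)) = 0.0214. Then 0.06/0.0214 = 2.80, and power on normal quantiles is 80.1%, which reproduces the stated 80%. With the 2K − 2 = 10 degrees of freedom available between schools, the same design has 71.5%. With 16 schools (14 df) it has 85.3%. These are the relevant starting values for a gain in precision.

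**2. How much of the error lies between schools.** Between-school SD = 0.22 × √0.02 = 0.031. Its contribution to the SD of the arm difference is 0.031 × √(2/6) = 1.8 percentage points with 12 schools, and 0.031 × √(2/8) = 1.6 with 16. These are 30% and 26% of the 6-point target. As a share of the variance of the arm difference it is 117 × 0.02 / 3.32 = 70%, whichever K applies.

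**3. Chance of imbalance under simple 1:1 allocation.** There are 924 ways to choose 6 of 12 schools and 12,870 ways to choose 8 of 16. Allocations that put at least one district wholly in one arm:

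| Schools | Assumed district sizes | Count | Chance |
|---|---|---|---|
| 12 | 2/2/2/3/3 | 780 of 924 | 84% |
| 12 | 4/2/2/2/2 | 828 of 924 | 90% |
| 16 | 3/3/3/3/4 | 7,362 of 12,870 | 57% |
| 16 | 6/4/2/2/2 | 10,950 of 12,870 | 85% |

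If half the schools are middle schools (assumed), a split of 5:1 or worse has chance 74/924 = 8.0% with 12 schools. A split of 6:2 or worse has chance 1,698/12,870 = 13.2% with 16.

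**4. What balancing could gain.** If a fraction f of between-school variance is removed and the analysis respects it, the design effect becomes 1 + 116 × 0.02 × (1 − f). For 12 schools:

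| f (assumed) | SE | Power, 10 df (no district terms fitted) | Power, 6 df (five districts fitted) |
|---|---|---|---|
| 0 | 0.0214 | 71.5% | 65.0% |
| 10% | 0.0206 | 74.6% | 68.0% |
| 25% | 0.0194 | 79.4% | 73.1% |
| 50% | 0.0173 | 87.9% | 82.4% |

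The 10-df column approximates a permutation test, which spends no model degrees of freedom. With 16 schools, fitting five districts (10 df) takes 85.3% to 83.0% if district explains nothing.

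**5. How tight the constraint may be.** With sizes 2/2/2/3/3, near-even balance in every district leaves 144 of 924 allocations. Assume six middle and six high schools spread across the districts. Requiring exactly three of each level per arm then leaves 50, so the smallest two-sided permutation p is 2/50 = 0.04. A third constraint that halved this would leave about 25 and a smallest p of about 0.08, so 0.05 could not be reached. Allowing level to be off by one school leaves 120. With sizes 4/2/2/2/2, near-even district balance alone leaves 96.

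**The case against.** The strongest reply is that the document is silent on the method. A reader might infer that randomization was unrestricted, but no section says so, and a balanced scheme may have been used without being described.

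A reader might also infer that districts apply different definitions of a contact. No section says that either. Tracing follows local and state guidance, all five districts are in one county, and school staff do part of the work. Practice may therefore be common to all districts, or may vary by school in a way that balancing on district would not remove. This stands: the mechanism is plausible but not documented.

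A third tempting reading is that the effect estimate is biased. It is not. Over repeated randomizations simple allocation is unbiased, and the ICC of 0.02 already puts between-school variance into the power calculation. What chance imbalance does is add variance and make a single allocation harder to interpret. One small district in one arm is also not a measure of error, because districts can offset one another.

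The covariate list gives partial cover. Age stands in for level among students, and masking, distancing, ventilation and exposure location capture some school practice. The list is open-ended, so district could be added. As written, though, nothing in it represents tracing practice.

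Finally, it may be too late. The version is dated May 2023, an entry dated 1.4.22 records completed work, and the June 2022 laboratory change was made so that testing could continue. This limits the remedy, not the point.

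**Conclusion.** The point holds as a matter of precision and of specifying the randomization, not as a finding of bias. The plan states a 1:1 ratio and no balancing factor for schools drawn from five districts and two levels, and omits both from the listed covariates. Under simple allocation a single-arm district would be more likely than not in all four splits examined (57% to 90%), but those splits are assumed.

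The figure that rests on the plan's own inputs is the 70% share of variance lying between schools. How much of it district and level explain is unknown, so the gain is a range: from 71.5% to about 75%, 79% or 88% power with 12 schools. A reader working on the plan's normal-quantile basis might claim 80% rising to 87% at a 25% reduction. That overstates both ends, because 12 schools give only 10 between-school degrees of freedom. If the factors explain nothing there is no gain, and fitting five district terms would lower power to 65%.

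**What to change.** If allocation is still open, replace the sentence in section E with covariate-constrained 1:1 randomization of schools on district and middle/high level:

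- Reconcile 12 versus 16 schools first, then list all allocations and keep those that meet stated balance limits.
- Set the limits loosely enough to keep a stated minimum number of allowed allocations, for example at least 100. Some district sizes will need looser limits to reach this.
- With 12 schools, do not add in-person enrolment as a tight third constraint.
- Test the arm effect with a permutation test over the allowed allocations, rather than by fitting five district terms.

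If schools are already allocated, do not rewrite the history. State the method actually used, apply the rule to any schools added later, and report arm by district and level. If simple randomization was used, run the permutation test over all 1:1 allocations.

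The cost is a randomization program, a paragraph of SAP text and fewer admissible allocations. No extra schools are needed. The change cannot alter allocations already made.

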In the initial CAB meeting, the best locations to perform symptomatic testing, both in the schools and in participating health centers was determined. Our CAB will be essential in addressing barriers to testing, follow-up care, and the importance of confidentiality. We will determine what information and resources are needed for individuals who test positive and address any concerns regarding confidentiality for these individuals. The CAB will meet at least monthly during the implementation of testing and more frequently if needed. Our team acknowledges that the success of this project will rely on these community partnerships and our maintenance of trust with these school communities. All of our community partners serve the families in the study school districts. In order to maintain the trust of the schools and the community, the research team will present study team updates to the CAB and superintendents at least monthly.

Description of milestones and timeline completion

The overall proposed project activities and timeline are shown in Table 2. Specifically, in the first-month post-award, the key dependencies include IRB approval, an initial meeting with the newly formed community advisory board (CAB), and development of the REDCap database structure required for saliva testing. Within 3 months, the key dependencies include schools returning to in-person learning and consenting of students and staff in the selected schools for screening testing. An important dependency for testing throughout the duration of this project will be the community case rate of COVID-19. Since the epidemiology and seasonality of this virus are still being defined, the volume of symptomatic testing could vary.

| Milestones/Project Activities | Year 1 | | | | Year 2 | | | |
|---|---------------|-----------|-----------|-----------|---------------|-----------|-----------|-----------|
| | Q1 | Q2 | Q3 | Q4 | Q1 | Q2 | Q3 | Q4 |
| Obtain IRB approval | • | | | | | | | |
| Submit to Clinicaltrials.gov | • | | | | | | | |
| Implement data coordination, collaboration, harmonization with RADx-UP CDCC | • | • | • | • | • | • | • | • |
| Convene Community Advisory Board meetings | • | • | • | • | • | • | • | • |
| Conduct monthly Superintendent meetings | • | • | • | • | • | • | • | • |
| Conduct symptomatic testing for all 12 schools | • | • | • | | | | | |
| Test & deliver messages for increasing uptake of SARS-CoV-2 testing | • | | | | | | | |

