Follow-up Protocols: Testing results will be available within 24 to 72 hours. All students, staff, and household members with positive results will be notified by [name] and/or a member of the study team and information regarding appropriate isolation and quarantining for contacts will be provided to comply with prevailing National/County health department recommendations. Additional financial and social services needed for the student and family due to isolation and/or quarantine procedures may be coordinated with the school and community partners. Finally, all positive individuals may have a 3-week phone call follow-up to inquire about the outcome of their illness including the need to seek medical attention and/or be hospitalized. For those in the contact arm, there might be additional questions if the

individual tests positive related to: activities, behaviors, and potential school based exposures.

Assessment of School Mitigation Strategies: Ascertaining the mitigation practices in place for each school is essential for evaluating the impact of additional testing on school transmission. A school-based mitigation strategy survey (Appendix 1), developed in conjunction with the CDC and utilized in prior school-based investigations, may be completed by each school at the beginning of the project. Questions in this survey will include: method of instruction (e.g., hybrid, type of hybrid, fully in-person) and date implemented, masking recommendations and perceived compliance, distancing in classrooms, use of physical barriers (e.g., Plexiglas), location and processes for eating lunch, and mitigation strategies used in extracurricular activities (e.g., sports, choir, band). Schools will also be asked about their quarantine rates and new school based cases/contacts on a weekly basis. This will help understand the rates of transmission in the schools.

Assessment of School-based Transmission: The primary outcome for this study will be the average of the secondary attack rate of school-based transmission per case at each school. For example, if a case has 10 contacts and 2 become infected, the secondary attack rate for that case would be 20%.

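### Sixteen schools are randomised in the procedures but power is given only for twelve; with school-level degrees of freedom the stated inputs give 85.3% for sixteen and 71.5% for twelve, not 80%

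*Combined protocol and SAP*

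**What the plan says.** The number of randomised schools has two values in the current version.

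**Twelve schools**
- Section A, Introduction: "12 middle and high schools from five predominantly African-American school districts".
- Section C, milestone table (Table 2): "Conduct symptomatic testing for all 12 schools".
- Section E, power calculation: "A cluster randomized trial (CRT) will be conducted at 12 schools", allocated 1:1.

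**Sixteen schools**
- Section C, Study Setting and Populations: "Sixteen middle and high schools from these school districts will participate".
- Section D1, Screening Testing: "Eight of the sixteen schools will be randomized to screening testing".

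The only power statement is in section E: "6 schools in each arm with an average of 117 participants per school will achieve 80% power". It assumes rates of 2% and 8%, ICC 0.02, SD 0.22 and a two-sided t-test at 0.05. Table 3 lists ten combinations of ICC and SD with the number of participants needed per school. Degrees of freedom are stated neither for this t-test nor for the planned GEE analysis with sandwich standard errors.

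Section D1 defines the primary outcome as "the average of the secondary attack rate of school-based transmission per case at each school", and section E also defines it as a ratio for each case. Table 3 counts participants.

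**The concern.** In a cluster randomised trial the number of clusters is the first element of the sample size, and here it is not settled. The milestone text in section C and the contingency text in section D1 allow schools or districts to be added. That may explain growth from 12 to 16, but neither place says that the randomised number became 16, and the power paragraph was not revised.

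The choice of degrees of freedom adds to this. Schools are randomised and everyone in a school receives the same assignment, so the treatment comparison rests on 12 or 16 independent units. With so few, the reference distribution matters, and the plan does not name it. On school-level degrees of freedom the two counts fall on opposite sides of the 80% target.

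Anyone working from section E would also expect the wrong number of schools, the wrong degrees of freedom and, at 117 per school, the wrong total (12 × 117 = 1,404 against 16 × 117 = 1,872) if the procedures are right.

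Two smaller gaps limit how far the figures can be read. It is unclear what the 117 counts, since the outcome is a rate per case. And 117 is given as an average with no allowance for schools of different size.

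**Working it through.** **Inputs (section E).** Difference 0.08 − 0.02 = 0.06; SD 0.22; ICC 0.02; m = 117 per school; two-sided alpha 0.05. Schools per arm: k = 6 (section E) or k = 8 (section D1). Equal school sizes unless stated.

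**Formulas.**
- Design effect: DE = 1 + (m − 1) × ICC = 1 + 116 × 0.02 = 3.32
- SE = SD × √(2 × DE / (k × m))
- Non-centrality = 0.06 / SE
- School-level df = 2(k − 1)

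**Reproducing the plan's 80% (k = 6).** SE = 0.22 × √(6.64 / 702) = 0.02140, so the non-centrality is 0.06 / 0.02140 = 2.804.
- Normal reference: 80.1%.
- t on participant-level df, 2(702 − 1) = 1,402: 80.0%.
- t on effective-sample df: 79.9%.

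All ten rows of Table 3 give 80.0–80.2% in the same way (normal reference, k = 6). The table was therefore built for 12 schools with a large-sample reference. Clustering enters the variance but not the degrees of freedom.

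**Changing the school count and the reference separately, at 117 per school.** For k = 8, SE = 0.22 × √(6.64 / 936) = 0.01853 and the non-centrality is 3.238.

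| Schools | Large-sample reference | School-level df |
|---|---|---|
| 12 (6 per arm) | 80.1% | 71.5% (t, 10 df) |
| 16 (8 per arm) | 89.9% | 85.3% (t, 14 df) |

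A simulated t-test on school means (200,000 runs, equal sizes) gave 71.7% and 85.1%, in line with the right-hand column. At their listed sizes, all ten Table 3 rows give 71.4–71.6% for 12 schools and 85.2–85.4% for 16 on school-level df.

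**What 80% would require on school-level df.**
- Base case: about 320 per school with 12 schools, or 77 with 16.
- Detectable difference at 117 per school: 6.7 points with 12 schools, 5.6 with 16.
- As m grows, DE/m tends to the ICC, so power has a ceiling. With 12 schools, five of the ten Table 3 rows cannot reach 80% at any school size (ICC/SD 0.01/0.35, 0.02/0.24, 0.02/0.25, 0.03/0.20 and 0.03/0.21; ceilings 73.1–78.8%). With 16 schools every row can (ceilings 86.6–99.4%).

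**Fixed total.** If 1,404 participants were spread over 16 schools (1,404 / 16 = 87.75 each), power would be 81.9% on 14 df, or 87.1% on the large-sample basis.

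**Unequal school sizes.** The documents give no coefficient of variation (CV), so these values are assumptions. The lower end of each range uses DE = 1 + ((1 + CV²) × 117 − 1) × 0.02; the upper end is a simulated t-test on unweighted school means. Both use school-level df.

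| CV | 16 schools | 12 schools |
|---|---|---|
| 0.3 | 83–84% | 69–70% |
| 0.5 | 79–82% | 65–68% |

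By the formula, 16 schools fall below 80% at a CV of about 0.47.

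**The case against.** The strongest reply is that section E is correct on its own terms. For 12 schools and a large-sample reference, the 80% and all of Table 3 reproduce. If the procedures describe the trial as it stands, power is above 80% at 117 per school on either reference (85.3% or 89.9%), and it stays above 80% with the total held at 1,404. On this view the power paragraph is merely out of date. A shortfall appears only if 12 is the true count and school-level df are adopted. Further, the planned analysis is a participant-level GEE with covariates, not a t-test on school means, so 71.5% is not strictly the power of that analysis.

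Much of this stands. There is no arithmetic error, and an inadequately powered trial is not shown if 16 is right. The like-for-like effect of the school count alone is 80.1% to 89.9%; the rest comes from the degrees of freedom.

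It does not remove the problem. The text gives two counts, and the only power statement belongs to one of them. Nor does the GEE make the small number of schools irrelevant: sandwich standard errors are estimated from the same 12 or 16 schools, and the plan names neither df nor a small-sample correction. If the school-level statistic follows a t distribution, a cut-off of 1.96 has a two-sided error of about 7.8% on 10 df and 7.0% on 14 df, rather than 5%.

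The questions of unit and unequal sizes are secondary. The conclusion does not depend on them.

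**Conclusion.** The concern holds. Current text gives both 12 and 16 randomised schools, and the stated 80% power belongs only to 12 schools with a large-sample reference. On school-level df the same inputs give 71.5% for 12 schools, about 8.5 points below target, and 85.3% for 16, about 5 points above it. The documents therefore do not show whether the trial meets its own power target.

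The contradiction in the count needs no assumption. The power figures rest on the plan's ICC, SD and difference, 117 units per school of the kind to which the SD applies, equal school sizes, and df equal to schools minus 2. It must be corrected because it concerns the number of randomised units.

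**What to change.** 1. Use one school count in the Introduction, the milestone table, Study Setting and Populations, the Screening Testing paragraph and the power calculation.
2. Recompute the power paragraph and Table 3 for that count with school-level df.
3. State the df, the unit counted per school (cases, contacts or participants, matching the unit to which the SD of 0.22 applies), and either equal school sizes or an assumed CV.

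Suggested wording: *Power is for [n] schools per arm, two-sided t-test on [2n − 2] df, ICC 0.02, SD 0.22 per [unit], difference 0.06, mean [m] [units] per school, assuming [equal school sizes / CV = x].* On the current inputs with equal sizes this gives about 85% at 117 per school for 16 schools and about 71.5% for 12.

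The cost is a change of protocol and SAP wording and one recalculation. No schools or participants are added. The stated power rises if 16 is the true count and falls if 12 is.
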